9.3 CLINICAL LABORATORY PROCEDURES

Not applicable.

9.4 OTHER PROCEDURES

A diagnostic *H. pylori* test (breath test, biopsy, or other test at the discretion of the Investigator)

[figure not shown]
Presence of *H. pylori* will be assessed at the EOS Visit. The selection of the method for this assessment is at the discretion of the Investigator.

10 ADVERSE EVENTS

Subjects receiving any investigational drug require careful observation. Any adverse event/concurrent illness experienced by a subject during any portion of the study must be described in detail and be fully evaluated by the Investigator. The Investigator is responsible for recording all adverse events observed or reported during the study from Inform Consent signature until date of completion/discontinuation, regardless of the drug-related assessment and/or clinical significance. Any pertinent information must be recorded in the CRF and additional comments describing the course and outcome of these events should be provided as appropriate.

10.1 DEFINITIONS

An Adverse Event (AE) is defined as any untoward medical occurrence in a subject or clinical investigation subject during the course of a clinical trial regardless of the causal relationship. The following flowchart illustrates the decision making process the Investigator should follow in determining how to document an AE in the study.

An **Unexpected Adverse Event** is defined as an adverse drug event, the nature or incidence of which is not consistent with applicable reference safety information (Pylera® SmPC [18 May 2012]; omeprazole Summary of Product Characteristics [February 2008]).

A **Serious Adverse Event (SAE)** is defined as any untoward medical occurrence that at any dose:

- Results in death; or
- Is life-threatening; or Requires inpatient hospitalization or prolongation of existing hospitalization excepting hospital admissions due to administrative reasons (e.g., the subject has no transportation home) or hospitalization for elective treatment of a pre-existing condition that did not worsen during the study unless a complication occurs during the hospitalization; or
- Results in permanent or significant disability/incapacity; or
- Results in congenital anomaly/birth defect.

Other important medical adverse events may also be considered serious, depending on the judgment of the Investigator or Aptalis Pharma US, Inc. (e.g., from ICH guidelines, intensive treatment in an emergency room or at home to prevent one of the outcomes listed in this

definition, blood dyscrasias or convulsions that do not result in hospitalization or development of drug dependency or drug abuse).

Note that as defined, serious events (expected or not) are not necessarily causally associated with the study treatment.

In addition, suspected transmission of infectious agents should always be considered as a SAE.

10.2 PRE-EXISTING MEDICAL CONDITIONS

Any pre-existing medical conditions, which do not worsen in duration, intensity or frequency during the study are not considered to be AEs. These pre-existing medical conditions should be adequately documented in the medical history of the CRF and any other appropriate ancillary documents. Pre-existing medical conditions, which worsen after exposure to study treatment will be recorded as an AE on the Adverse Event Form of the CRF.

10.3 LABORATORY TEST ABNORMALITIES

During the course of the study, the Investigator will be required to comment on any laboratory values outside the normal reference range. A laboratory abnormality should be regarded as an AE and recorded on the Adverse Event Form of the CRF if, according to the Investigator's judgment, the value is significantly worse than at pretreatment and has been confirmed by repeat testing, when applicable. In addition, an abnormal laboratory test value discovered after ICF signature and that was not previously known should be considered as an AE.

10.4 GUIDELINES AND EVALUATION

To promote consistency between sites, the following guidelines should be taken into consideration along with good clinical judgment when documenting and recording AEs.

10.4.1 Assessment and Recording

An AE, whether or not considered causally related to the treatment, must be promptly documented and recorded. At each study visit, after the subject has had an opportunity to spontaneously mention any problems, the Investigator should inquire about AEs by asking the appropriate open questions. In addition to straightforward subject observation (e.g., headache, nausea, etc.), AEs will also be documented from any data collected in the CRF (e.g., laboratory values, physical examination findings, etc.) or other documents (e.g., subject diaries) that are relevant to subject safety.

At each follow-up visit or assessment by phone or otherwise, all AEs, whether observed by the Investigator or one of his or her professional collaborators, or reported by the subject

spontaneously or in response to an open question, will be recorded in the Adverse Event Form included in the CRF with the following information.

- **Name of the AE:** Name should be a medical term. When possible, the Investigator should differentiate an illness entity from isolated symptoms or signs. For instance, the term “flu” should be recorded instead of listing all the flu-related symptoms. Where a differentiation is not possible, symptoms and signs should be separately recorded and evaluated as **Adverse Events**.
- **Start date and stop date (or statement that the event is continuing) of the AE**
- **Imputability of Pylera®:** evaluate the causal relationship between Pylera® and the AE as described in section 10.4.2
- **Seriousness criteria** as defined in section 10.1

The Aptalis Pharma US, Inc CRA who visits the center will check the completeness and accuracy of the Adverse Events Form. Wherever possible, all AEs regardless of the seriousness must be followed through resolution.

10.4.2 Causality Assessment

Part of the Adverse Event documentation will involve the Investigator making a causality assessment. To promote consistency between Investigators, the following guidelines should be taken into consideration along with good clinical judgment when determining the relationship of study medication to adverse event.

The following criteria can be used in order to evaluate the causal relationship between the study medication and the AE.

No reasonable possibility	 The AE is definitely not associated with the study treatment AND/OR  The AE does not follow a reasonable temporal sequence from drug administration AND/OR  The AE does not disappear or decrease on discontinuation of the study drug (dechallenge) and/or does not reappear or increase on repeated exposure (rechallenge) AND/OR  The AE is reasonably explained by known characteristics of the patient’s clinical state, history, environment, other therapy administered to the patient (drug or non-drug) AND/OR  The AE may be caused by reasons other than administration of the study drug
Reasonable possibility	 The AE follows or may follow a reasonable temporal sequence from study treatment AND/OR  The AE disappears or abates upon discontinuation of the study treatment (dechallenge) and/or reappears or increases on repeated exposure (rechallenge)

AND/OR

- The AE cannot be reasonably explained by known characteristics of the patient's clinical state, history, environment, other therapy administered to the patient (drug or non-drug) AND/OR
- Previous experience with the study medication or related compounds resulted in a similar event AND/OR
- The AE is a known effect of the study treatment

10.4.3 Reporting Requirements

10.4.3.1 Serious Adverse Events

All SAEs, regardless of relationship to study treatment, must be reported by the Investigator to Aptalis Pharma US, Inc. by completing the SAE form of the CRF within 24 hours of awareness. This includes SAEs occurring as soon as the subject signs the Informed Consent (i.e. pre-treatment SAEs). The SAE form should be completed as thoroughly as possible, given the information available and time constraints. Upon completion, the SAE form should be signed by the Investigator or sub-Investigator using the CRF. SAEs which could be associated with the trial procedures and which could modify the conduct of the trial are reportable within 24 hours.

In addition, any spontaneously reported Serious Adverse Events (SAE: details in sections 10.1 and 10.5) that occurs within 30 days after the last study procedure or study drug administration should be recorded in the SAE form provided in the ISF.

The SAE Form should be completed as thoroughly as possible, given the information available and time constraints, signed and faxed or emailed to Aptalis Pharma US, Inc. (Drug Safety department, contact details provided within the ISF).

Email: [contact]

Death and surgery should not be reported as an event. Death and surgery are viewed as an outcome of an event, rather than the event itself. In cases where the cause of death is unknown, death may be initially reported as an event. Every attempt should be made to submit a follow-up report identifying the cause of death.

SAEs will be monitored by Aptalis Pharma US, Inc. in real time throughout the trial.

10.4.3.2 Adverse Events

All AEs will be reported on the Adverse Events Form of the CRF.

10.4.3.3 Other reportable events

The following events will be recorded and reported within 24 hours to Aptalis Pharma US, Inc. as described in Section 10.4.3.1:

- Any pregnancy that occurs in study subjects or their partners during the study should be recorded and reported to Aptalis Pharma US, Inc. using the appropriate Pregnancy Surveillance Form provided in the CRF. If a pregnancy occurs in a subject during the study, the administration of the investigational product must be discontinued. Follow-up should be ensured to collect information about the course of the pregnancy and delivery, as well as the condition of the newborn. When the newborn is healthy, additional follow-up is not needed. In case of health problem in the newborn, follow-up must be performed as described in section 10.5. The Investigator will provide follow-up information concerning the outcome of pregnancy to the sponsor in a timely manner.
- The following should be recorded and reported on the appropriate form provided in the CRF:
 - Drug abuse, misuse and overdose with or without AEs (an overdose is a dose higher than that prescribed by a health care professional for clinical reasons. It is up to the participating Investigator to decide whether a dose was an overdose).
 - Inadvertent or accidental exposure to the investigational product with or without an AE should be recorded and reported to Aptalis Pharma US, Inc.
 - Any other medication errors (including dispensing errors such as inadvertent use of expired medication and dosing errors) with or without an AE.
 - Suspected transmission of an infectious agent.

There will be additional follow-up for neurological adverse events indicative of encephalopathy through a separate and concomitant safety program, i.e. the Intensive Monitoring Program, as part of Risk management plan of Pylera. A “Pharmacovigilance reporting form – for neurological events with bismuth” shall be completed for each case where neurological symptoms listed in the Appendix 3, accompanied or not by bismuth whole blood concentrations above 50 µg/L occur. There will be a case review and confirmation by the Scientific Committee of the Intensive Monitoring Program for the diagnosis of encephalopathy. The assessment of the correlation between bismuth concentration and occurrence of neurological symptoms will be provided in the Periodic Safety Update Reports (PSUR) and in the reports from the Intensive Monitoring Program.

10.5 FOLLOW-UP AND FINAL REPORTS

The clinical condition of human subjects who have had a SAE must be followed until all parameters, including laboratory values, have either returned to normal or to baseline value or are

otherwise explained or judged acceptable by the Investigator. Follow up and/or Final Reports, including information on the action taken and the outcome, must be sent to Aptalis Pharma US, Inc.

In the event of death, any post-mortem findings (including histopathology, autopsy report) must be provided to Aptalis Pharma US, Inc.

If the follow-up information is received after the last study procedure or last study drug administration, this information will not be recorded in the CRF but should be provided to Aptalis Pharma US, Inc. using the Aptalis Pharma US, Inc. SAE form provided in the ISF.

10.6 REGULATORY ASPECTS

Aptalis Pharma US, Inc. has a legal responsibility to notify the HPFB of Canada, the FDA of the United States of America, the EMA, and the National Competent Authorities and Central Ethics Committees of European Union, and all other foreign regulatory agencies as well as all sites about the safety of the drug. The Investigator has the responsibility to notify the local Ethics Committee about SAEs.

The Investigator(s)/institution(s) will permit trial-related monitoring, audits, IRB/IEC review and regulatory inspection(s), providing direct access to source data/documents. Copies of the notification to the ethics committee must be sent to Aptalis Pharma US, Inc.

10.7 DATA SAFETY MONITORING BOARD

No Data Safety Monitoring Board is planned for this study.

Subjects who demonstrate a neurologic AE indicative of bismuth toxicity, will be evaluated by the Scientific Committee of a separate Intensive Monitoring Program. Such neurologic AEs of interest will include but are not limited to disorders in walking, speech and writing with psychiatric symptoms including mental confusion and myoclonia, tremor, and lack of coordination.

Subjects who demonstrate bismuth accumulation at the End of Treatment Visit ($> 50 \mu\text{g/L}$) will be requested to immediately return to the laboratory to draw a third blood sample for evaluation of bismuth. If bismuth concentration remains sustained and subject interview with Investigator confirms that no third-party source of bismuth was consumed outside of the context of this study,

	Page 41 of 96
	Protocol # : MA-PY-HpPK11-01

the subject will be referred to the separate Intensive Monitoring Program to be evaluated for inclusion.

The threshold for potential bismuth accumulation will be the Hillemand *et al.*²⁷ alert value of 50 µg/L, which will be defined as any accumulation value that is higher than 50 µg/L under the following formula:

$$\text{Accumulation Value} = (\text{EOT bismuth concentration} - \text{Day 0 bismuth concentration})$$

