
Study Procedures:
	
This is a single-arm, open-label trial in presumed H. pylori-positive subjects and is restricted to centers in France.
 
Following identification of participating general practice and specialist study centers, subjects deemed eligible for study will be identified and may be enrolled. To assess eradication, subjects will complete a diagnostic H. pylori test (breath test, biopsy, or other test at the discretion of the Investigator) following a period of at least 28 days after the end of treatment.
 
Subjects who are treatment-eligible will already have a prescription for Pylera® and a PPI (presumed to be omeprazole) and will have been instructed on dosing as the dosing information contained within the Pylera® SmPC: 3 capsules Pylera® QID taken after meals and following a bedtime snack, and omeprazole capsule BID taken after breakfast and evening meal doses of Pylera®, for 10 days (equivalent to daily doses of 480 mg [as Bi₂O₃ equivalent], tetracycline hydrochloride 1500 mg, metronidazole 1500 mg, and omeprazole 40 mg).
 
Subjects will provide two blood samples for assessment of bismuth concentrations (total bismuth in plasma and whole blood and trimethylbismuth (TMB) in whole blood), with one sample provided prior to start of Pylera® treatment (D0) and one sample provided Day 11 i.e. Day 1 after completion of Pylera® treatment. If accumulation of bismuth is detected (defined as whole blood bismuth concentration exceeding 50 µg/L.), subjects will be contacted to immediately return to the laboratory to draw a third verification sample and will be referred for potential inclusion and follow-up in a separate intensive monitoring program. In case of a neurological AE indicative of bismuth encephalopathy (please refer to Appendix 3 – Central Nervous System Adverse Events of Interest) is present at Day 11 blood samples will be as quickly processed as possible.

	
A diagnostic H. pylori test to assess H. pylori eradication should be repeated on one single occasion at least 28 days post-treatment.

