3.2 SCHEDULING OF VISITS

Patient inclusion in the study will be considered after the decision to treat with Pylera® has been made by the Investigator.

The Inclusion Visit will be initiated following signature of Informed Consent.

Information regarding date of Pylera® prescription, name of prescribed PPI, demographic data, vital signs, height, weight, disease history for *H. pylori* infection (including information pertaining to prior *H. pylori* treatment), co-morbidities, medical and surgical history — will be surveyed, as well as information concerning diagnostic procedures performed to verify *H. pylori* infection.

Upon confirmation of eligibility, subjects will be given instructions for the first blood sample (D0 sample) for bismuth and TMB PK prior to initiating treatment with Pylera®, and an appointment for the second blood sampling.

Upon completion of the 10-day treatment with Pylera®, subjects will proceed to the EOT Visit to provide the second blood sample (D11 sample) for bismuth and TMB PK.

Subjects who demonstrate clinical symptoms indicative of bismuth-related neurological adverse events or bismuth accumulation at the EOT Visit (total bismuth in whole blood > 50 µg/L) will be requested to return to the laboratory immediately to draw a third blood sample for evaluation of bismuth. Subjects having clinical symptoms indicative of bismuth-related neurological adverse events will be referred to the separate Intensive Monitoring Program. If bismuth concentration remains sustained in subjects with no neurological symptoms and subject interview with Investigator confirms that no third-party source of bismuth was consumed outside of the context of this study, the subject will be referred to the separate Intensive Monitoring Program to be evaluated for inclusion.

A diagnostic *H. pylori* test (breath test, biopsy, or other test at the discretion of the Investigator) to assess *H. pylori* eradication should be repeated on one single occasion at least 28 days post-treatment as part of the EOS Visit.

Vital signs, concomitant medications, adverse events (AEs) and the presence of central nervous system (CNS) adverse events of interest as listed in Appendix 3 will be assessed at the EOT and EOS Visits.

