9.2.1 Subjects who completed treatment with Pylera®

Subjects who have completed the 10-day treatment with Pylera® will return to complete the following procedures as part of the EOT Visit:

- Vital signs measurement (blood pressure, pulse rate)
- Recording Pylera® treatment description and compliance
- Recording of concomitant medications
- Recording of AEs

The presence of CNS adverse events of specific interest as listed in Appendix 3 will be assessed at this visit with the specific form “Pharmacovigilance reporting form-neurological disorders and bismuth” developed for the collection of the adverse events of special interest as part of the Intensive Monitoring Program that will be completed by the Investigator.

Subjects will provide one blood sample as the post-treatment sample (D11 sample) for assessment of plasma and whole blood bismuth concentrations as well as whole blood TMB concentrations as per the procedures outlined in Appendix 2.

Subjects who demonstrate bismuth accumulation in whole blood at the EOT Visit ($> 50 \mu\text{g/L}$) will be requested to return immediately to the laboratory to draw a third blood sample for evaluation of bismuth. If bismuth concentration remains sustained and subject interview with Investigator confirms that no third-party source of bismuth was consumed outside of the context

of this study, the subject will be referred to the separate Intensive Monitoring Program to be evaluated for inclusion.

Subjects will return 28 days after the EOT Visit to complete the EOS Visit. At this visit, subjects will complete:

- Vital signs measurement (blood pressure, pulse rate)
- Recording eradication test
- Recording of concomitant medications
- Recording of AEs

The presence of CNS adverse events of specific interest as listed in Appendix 3 will be assessed at this visit with the specific form “Pharmacovigilance reporting form-neurological disorders and bismuth” developed for the collection of the adverse events of special interest as part of the Intensive Monitoring Program that will be completed by the Investigator.

Subjects who demonstrate a positive diagnostic *H. pylori* test (breath test, biopsy, or other test at the discretion of the Investigator) at End of Study will be documented by the completion of a specific form entitled “Targeted follow-up form – Pylera® eradication therapy failure”. These subjects will be referred to treatment for *H. pylori* infection outside of the context of this study.

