11.7.7 Pharmacokinetic / Pharmacodynamic Analysis

This study will focus on the detection and assessment of bismuth concentrations within the circulating plasma and whole blood compartment.

The initiation of any encephalopathy by an external compound requires the absorption of the material(s) and its transport to the central nervous system and its eventual crossing of the blood-brain-barrier; material which is not absorbed and eventually excreted in the feces will have no potential to induce an encephalopathy.

It is not known which metabolite(s) (if any) bismuth subcitrate potassium transforms to following ingestion of Pylera® by patients, and how such metabolites are further transformed. In the context of the clinical cases reported in the 1970s, it was never confirmed which bismuth metabolites generated the bismuth-associated encephalopathies.

One metabolite – trimethylbismuth (TMB) – is produced by methanoarchaea bacteria^{31,32,33} present within the intestinal flora and is detectable at picogram levels within the circulating plasma compartment and by examination of respiratory exhalation³⁴. TMB has been implicated in

bismuth-associated encephalopathies following the demonstration of encephalopathies in experimental animals exposed by inhalation to large uncontrolled quantities of TMB³⁵.

The detection of total bismuth (metal) rather than individual bismuth metabolites permits the detection of all bismuth circulating within the bloodstream irrespective of whatever metabolite form the bismuth atom is found in. Whole blood TMB will be evaluated using an analytical method derived from Boertz *et al.* (2009)³⁴ due to the possibility of encephalopathy arising from animal models. Post-treatment plasma and whole blood concentrations of bismuth (metal and TMB) will be described after subtraction of the baseline value for each subject using the following formula:

$$\text{Accumulation Value} = (\text{EOT bismuth concentration} - \text{Day 0 bismuth concentration})$$

This comparison will include an evaluation of bismuth concentration in subjects who report neurological AEs and subjects who do not report neurological AEs.

After comparison on the whole sample, data will be stratified by the PPI used in combination with Pylera® and the comparison will be repeated in strata where sample size allows.

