An additional comparison will be made of all post-treatment concentrations in the omeprazole group versus post-treatment concentrations of all other PPIs pooled together. For each subject the C_{\min} will be grossly estimated assuming an elimination half-life of 19.95 hours³⁰ by the equation:

$$C_{\min} = \frac{C_{\text{observed}}}{e(-0.0347 * t)}$$

where t is the time elapsed between last dose intake and sampling time.

Individual observed results will also be classified as “above” or “below” the Hillemand *et al.*²⁷ alert threshold of 50 µg/L²⁷ for total whole blood bismuth concentrations solely as TMB has been calculated by Aptalis Pharma US, Inc. to exist at approximately 1:10,000 the level of average circulating bismuth concentrations.

For subjects who are already below 50 µg/L on Day 11, no other action will be performed and such subjects will be considered to have reached safe whole-blood levels within an acceptable time.

For subjects who are above 50 µg/L, the time required to reach 50 µg/L will be grossly estimated, again assuming an elimination half-life of 19.95 hours by the equation:

$$T_{recov} = \frac{\ln\left(\frac{50}{C_{min}}\right)}{-0.0347}$$

Such subjects will also be referred for evaluation and potential inclusion in the separate Intensive Monitoring Program.

The number of subjects requiring more than 24 hours to reach safe levels and the time required will be considered to draw conclusion on the clinical safety of Pylera® with regard to bismuth toxicity.

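### Accumulation above 50 µg/L has two definitions: Section 10.7 cuts on end-of-treatment minus Day 0, the rest of the protocol on the observed whole-blood level

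*Protocol*

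**What the plan says.** The current protocol text uses 50 µg/L in two ways.

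**Observed level at end of treatment (EOT).**
- The synopsis (Study Procedures) treats accumulation as detected when it is "defined as whole blood bismuth concentration exceeding 50 µg/L".
- Section 3.2 has "bismuth accumulation at the EOT Visit (total bismuth in whole blood > 50 µg/L", and Appendix 2 (additional third sample) states the same criterion.
- Section 9.2.1 recalls "Subjects who demonstrate bismuth accumulation in whole blood at the EOT Visit" when the level is above 50 µg/L.
- Section 11.7.7 says "Individual observed results will also be classified as" above or below 50 µg/L, for total whole-blood bismuth only.

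**Difference from Day 0.**
- Section 10.7 ties the threshold to the alert value, "which will be defined as any accumulation value that is higher than 50" µg/L, with the accumulation value equal to the EOT concentration minus the Day 0 concentration. It does not say whether plasma or whole blood is meant. The sentence directly follows the text on the third sample and on referral to the Intensive Monitoring Program.
- Section 11.7.7 uses the same formula, but only for description: concentrations "will be described after subtraction of the baseline value for each subject using the following formula". No cut is attached there.

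Section 1.1 introduces the alert value as a sustained blood concentration above 50 µg/L, which is an absolute level.

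**The concern.** The primary objective (Section 2.1) is to verify that bismuth does not accumulate, so the protocol needs one meaning of accumulation. Section 10.7 takes an alert value that Section 1.1 defines on an absolute level and applies it unchanged to a change from baseline. The two rules are not interchangeable, and the difference rule is the less sensitive of the two.

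Two things depend on which section is followed: whether a subject without neurological symptoms is recalled and referred, and how many subjects the report describes as showing accumulation.

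Non-zero baselines are possible by design. Section 4.2.2 does not exclude prior bismuth exposure, Section 9.1.2 records previous *H. pylori* treatment without excluding it, and Section 1.2 says the study is meant to capture misuse and concomitant use of other medications.

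**Working it through.** **Inputs**
- Threshold: 50 µg/L (synopsis, 3.2, 9.2.1, 10.7, 11.7.7, Appendix 2).
- Elimination half-life 19.95 h and rate constant 0.0347 per h (11.7.7).
- Time from the Day 0 sample to the EOT sample: about 11 days = 264 h, with 240 h and 288 h as sensitivity values.
- Day 0 concentration, D0: not given in the protocol. The values below are assumptions, shown as a range.

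**Step 1: the plan's own constant.** k = ln(2)/19.95 = 0.03474 per h, which rounds to the stated 0.0347. The plan's figure is reproduced.

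**Step 2: which subjects each rule flags.**
- Observed rule: EOT > 50.
- Section 10.7 rule: EOT − D0 > 50, that is EOT > 50 + D0.

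Since D0 ≥ 0, EOT − D0 > 50 implies EOT > 50, but the reverse does not hold. The 10.7 rule never adds a subject and misses all those with 50 < EOT ≤ 50 + D0.

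| Assumed D0 (µg/L) | Effective cut on EOT under 10.7 (µg/L) | EOT values flagged by the observed rule only |
|---|---|---|
| 0 | 50 | none |
| 1 | 51 | above 50, up to 51 |
| 5 | 55 | above 50, up to 55 |
| 10 | 60 | above 50, up to 60 |
| 20 | 70 | above 50, up to 70 |

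With assumed EOT 55 and D0 10, the observed rule flags the subject. The difference is 55 − 10 = 45, so 10.7 does not. With EOT 60 and D0 5 the difference is 55 and both rules flag.

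**Step 3: does full subtraction fit the plan's kinetics?** If the Day 0 bismuth is a residue that decays with no further outside intake, the fraction left at time t is exp(−0.0347 t):
- 240 h: exp(−8.328) = 0.00024, or 0.024%
- 264 h: exp(−9.161) = 0.00011, or 0.011%
- 288 h: exp(−9.994) = 0.00005, or 0.005%

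A D0 of 10 µg/L would leave 10 × 0.000105 ≈ 0.001 µg/L at 264 h. A subtraction consistent with the plan's half-life would cut at EOT > 50.001 µg/L, whereas 10.7 cuts at 60. Under this condition 10.7 removes bismuth that is no longer in the EOT sample.

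**Step 4: what does not depend on 10.7.** In 11.7.7 the above/below classification uses observed whole-blood values. The minimum concentration and recovery time are computed from the observed concentration without subtracting Day 0. Neither changes with the 10.7 definition.

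**The case against.** - **The practical effect may be small.** Section 1.1 reports that subjects on full dosing in the Phase I study had an average 24-hour trough plasma level of 4.66 µg/L and no sustained level above approximately 20 µg/L. An untreated Day 0 level of 10 or 20 µg/L would be unusual unless the subject had taken other bismuth. This stands: the direction of the discrepancy is certain, its frequency is unknown.
- **Subtraction can have a purpose.** If outside bismuth intake continues unchanged through Day 11, the baseline persists and the difference isolates the rise due to treatment. This stands against an unconditional appeal to the half-life, which 11.7.7 itself uses only for gross estimation. It does not turn the difference into the absolute level described in 1.1. Section 10.7 also already addresses outside bismuth by interview.
- **A single Day 11 sample is not a sustained concentration either.** This is fair: neither rule reproduces the alert value exactly. It does not remove the conflict between them.
- **A reader might infer that the final safety conclusion is compromised.** The documents do not support that. Section 11.7.7 classifies observed values and bases its conclusion on the number of subjects needing more than 24 hours to reach safe levels, from unsubtracted values. A subject in the gap would still be listed as above 50 µg/L there, and a site following 3.2 or 9.2.1 would still recall that subject.
- **A reader might also infer that subjects with neurological symptoms could be missed.** Sections 3.2 and Appendix 2 provide for a third sample on symptoms alone, so the conflict concerns subjects recalled on concentration only.

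**Conclusion.** The contradiction is real and stands in the current text. Section 10.7 defines accumulation on EOT minus Day 0 with no named matrix; five other places use the observed EOT whole-blood level. The 10.7 rule is never more sensitive, and it raises the effective cut from 50 to 50 + D0 µg/L. That much follows from D0 being non-negative and needs no further assumption.

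How many subjects fall in the gap cannot be derived from the protocol. If baselines are near zero, there will be few or none. The statement that full subtraction over-corrects, because only about 0.01% to 0.02% of the Day 0 level remains after 240 to 264 h, rests on Day 0 bismuth being a decaying residue and fails under continuing outside intake.

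What is left undetermined is the concentration trigger for recall and referral, and the meaning of accumulation in the statement on the primary objective. The 11.7.7 classification and recovery-time estimate are unaffected.

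**What to change.** Reconcile the synopsis, Sections 3.2, 9.2.1, 10.7 and 11.7.7, and Appendix 2 to one definition of accumulation and one named matrix. Which concentration triggers the third sample and referral is a clinical matter for the sponsor to reconcile; no rule is proposed here.

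For the analysis:
- report the 50 µg/L classification on the observed EOT whole-blood level, as 11.7.7 already states;
- keep EOT minus Day 0 as a descriptive change with no 50 µg/L cut, also as 11.7.7 already has it;
- list every subject whose classification differs between the two definitions, with the Day 0 and EOT values.

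The cost is wording, mainly in 10.7, and one short listing. Both samples are already taken, so no extra data are needed.
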